10.2. Informed Consent

All subjects must sign the study-specific IRB/REB-approved Informed Consent/HIPAA Form; see **Section 8.3**. The original signed Form is to be placed in the subject's study file. A copy of the signed Form is also to be given to the subject for their records.

10.3. Subject Diary

The Subject Diary serves as a tool for the subject to record pre- and post-treatment health and information. The Subject Diary is reviewed for solicited event occurrence and severity, changes to medications, occurrence of adverse events, and possible recurrence of CDI. The subject also documents changes in medications.

At the Screening visit, subjects are provided a Subject Diary to complete each day until the day prior to the study enema (Baseline visit). This may be up to 21 days. The diary will be reviewed at the Baseline visit prior to enema administration.

Prior to the subject leaving at the conclusion of the Baseline visit, the subject is instructed to continue completing the Subject Diary for each day until the 1-week office visit.

The following information is entered into the study database:

- solicited event severity
- changes to medication
- occurrence of adverse events

10.4. Optional Stool Samples for Additional Testing by Rebiotix

Subjects may agree (consent) to provide additional, optional stool samples to Rebiotix for research development activities. Subjects consenting to the Optional Stool Sample collection are requested to provide stool samples directly to Rebiotix at the following time-points:

- Screening (between the time of enrollment and prior to treatment)
- at the time of the 1- and 8-week office visits
- at the time of the 4-week, and at 4- and 6-month phone calls
- at the time of possible treatment failure symptoms
- at the 1-, 4-, and 8-weeks and 6-month phone calls after a second enema, if applicable

Subjects collect the samples at home in pre-labeled containers given to them by the study team. Rebiotix provides the study sites with kits containing all the materials for collecting and shipping the samples, including subject directions, container labels, and prepaid, pre-addressed mailing labels. Samples are identified by the label on the container that contains only the subject's study identification number and date/time of the sample; samples will not contain any personal information that would identify the subject. Samples may be stored for approximately five years. The stool samples will be used for research about the microorganisms in the human gut and the effects of microbiota restoration therapy on the gut microbiome. Some of the research will include testing for microorganisms (*Clostridium difficile* and vancomycin-resistant enterococci) both before and after receiving the study enema. Failure to send in a sample does not result in a protocol deviation, however subjects should be reminded of this request.

10.5. Screening Visit

The following study activities/data will be collected/conducted at the Screening visit:

- Subjects are told about the study and informed consent is obtained (enrollment)
- Assign the subject number.
 - The format for subject number will include site code, followed by study-specific identifier, and 3-digit subject number assigned in sequential ascending order. For example: AAAOLS, RBX08-###. Where “AAA” is your study site’s code, and “###” is the subject’s number following a -001, -002, -003,... format.
- Standard demographics: gender, ethnicity, date of birth, race
- Relevant medical history, including comorbidity index variables (see **Section 16**)
- CDI medical history documentation will be collected
- Assess inclusion/exclusion criteria
- Measure vital signs: height, weight, blood pressure, pulse, breathing rate and temperature
- Physical exam (no genitourinary exam unless medically indicated) is performed to establish a study baseline health status (findings that can be attributed to the subject’s medical history):
 - General
 - HEENT (head, eyes, ears, nose and throat)
 - Cardiovascular
 - Gastrointestinal

- Musculoskeletal
- Neurological
- Blood samples are collected and analyzed at the central laboratory for:
 - CD4 count
 - CBC w/differential
 - Comprehensive metabolic panel (CMP): Sodium, potassium, chloride, BUN, creatinine, albumin, AST, ALT, alkaline phosphatase, bilirubin (direct, indirect and total), glucose
 - C-reactive protein (CRP)
- NOTE: the results of the absolute neutrophil count (ANC) and CD4 tests must be confirmed ≥ 1000 cells/ μ L and $\geq 200/\text{mm}^3$, respectively*
- Onsite urine pregnancy test for subjects of child bearing potential
- Complete the Cdiff32 health-related quality of life questionnaire completed by the subject (see **Section 17**)
- Document concomitant medications taken within the last 30 days
- Completion of the Subject Diary is explained and how to complete it is demonstrated; see **Section 10.3**
- Record employment status
- For subjects who consented to the Optional Stool Sample collection, remind them to obtain and ship a stool sample to Rebiotix anytime between their Screening visit and their Baseline visit dates

10.6. Randomization

There is no randomization in this study.

10.7. Order IP/Study Drug

Orders for IP/study drug are placed through the Medpace ClinTrak study database. IP should be ordered approximately four (4) business days in advance of the planned IP administration date, if not earlier. This timeframe is to accommodate the shipping schedule, and instructions for thawing which are located in the Instructions for Use.

10.8. Baseline Visit and Study Treatment Administration

IP/study drug should be ordered approximately four (4) business days in advance of the planned IP administration date, if not earlier.

The Baseline visit is performed on the day of the study treatment (IP) administration. IP administration must occur within 21 days of the Screening visit. Antibiotics for the control of CDI symptoms are continued until 24-72 hours before administration of the IP.

The following study activities/data will be collected at the Baseline visit prior to IP administration:

- Inclusion/exclusion criteria are confirmed including the following:
 - The control of symptoms during antibiotic use is confirmed by review of the subject diary (see **Section 7.3.1**)
 - Compliance to the washout period (discontinuation of the antibiotics for 24-72 hours prior to the Baseline visit) is confirmed
 - Stop date and time (AM/PM) of antibiotic
- Central laboratory blood sample collection; see **Table 10-2** for the list of tests. *NOTE: these results are not needed before proceeding to treatment per the protocol*
- Central laboratory stool sample collection; see **Table 10-2** for the list of tests. *NOTE: the results are not needed before proceeding to treatment per the protocol*
- Onsite urine pregnancy test for subjects of child bearing potential
- Assess vital signs: temperature, pulse, blood pressure, respiration
- Changes to concomitant medications since the last visit
- Review subject diary (see **Section 10.3**)
- Assess recurrence of CDI
- Assess for adverse events since enrollment
- Date and time of the last bowel movement prior to the enema
- Did the subject void his/her bladder prior to entering the administration room

Table 10-2: Baseline Testing Conducted by Central Laboratory

Test Name	Material Tested
Norovirus	Stool
Rotavirus	
Adenovirus	
Enteric pathogens (Shigella , Salmonella , Campylobacter , sorbitol-negative E. coli ., Aeromonas , Plesiomonas , Yersinia , and shiga toxins)	
Giardia antigen	
Cryptosporidium antigen	
Acid-fast staining (Cyclospora, Isospora)	
Ova and parasites	
Vancomycin-resistant enterococci (VRE)	
Methicillin-resistant Staphylococcus aureus (MRSA)	
Extended spectrum beta-lactamase (ESBL)-producing Enterobacteriaceae	
Vibrio	
Listeria	
Clostridium difficile	
Carbapenem-resistant Enterobacteriaceae Culture (CRE)	
CBC with Differential	Blood
HIV	
Hepatitis A (IgG)	
Hepatitis B Anti-Hepatitis B surface antigen	
Hepatitis C Antibody	
Treponema Antibody	

The following information is collected specific to the administration of the IP:

- Enema clinical batch number
- Enema administration start and end time
- Enema administration status (successful; attempted, not completed; opened, not administered)
- Subject position for enema
 - Length of time subject was in position after enema
- Did the Rebiotix kit components perform as expected
- Note whether the subject expelled or leaked any of the IP during the observation period

- How long was the enema retained before the expulsion or leakage (minutes)
- What was the estimated amount of enema that was expelled or leaked

Following successful completion of the above listed items, IP is administered via enema per the Instructions for Use and standard site procedure; see **Section 9.8.3**. Subjects remain at the site under supervision for at least one hour post-IP administration for vital sign assessment (temperature, heart rate, blood pressure, respiratory rate) about every 15 minutes and observation. If the subject's vital signs do not return to the pre-administration values $\pm 20\%$, assess the subject for a possible AE.

All safety data collected are to be recorded and reported as required in **Section 11**.

The subject is sent home after completion of study procedures including a review of the Subject Diary instructions, and is requested to call the study site if symptoms recur or at the onset of an adverse event.

10.9. 1-week In-Office Visit

The 1-week follow-up visit is to occur within the window of ± 3 days from the Baseline visit. All safety data collected are to be recorded and reported as required in **Section 11**.

The following study activities/data is collected at the 1-week follow-up visit:

- Review of the subject diary for solicited events as defined in **Section 11.4**
- Assess recurrence of CDI
- Subject's weight
- Adverse event collection, including new onsets of obesity, metabolic syndrome, pre-diabetes, diabetes and/or autoimmune disorders
- Cdiff32 health-related quality of life questionnaire completed by the subject
- Changes to concomitant medications since the last visit
- For subjects who consented to the Optional Stool Sample collection, remind the subject to collect and ship a stool sample to Rebiotix

10.10. 4-week Telephone Assessment

This phone call must occur within the window of ± 3 days (see **Table 10-1**); out of window or missed telephone assessments are to be reported as protocol deviations. All safety data collected are to be recorded and reported as required in **Section 11**.

The following study activities/data is collected at the telephone assessment calls:

- Assess recurrence of CDI
- Subject's weight, self-reported
- Adverse event collection, including new onsets of obesity, metabolic syndrome, pre-diabetes, diabetes and/or autoimmune disorders
- Changes to concomitant medications since the last visit
- For subjects who consented to the Optional Stool Sample collection, remind the subject to collect and ship a stool sample to Rebiotix

10.11. 8-week In-Office Visit

The 8-week follow-up visit is to occur within the window of ± 3 days (see **Table 10-1**). All safety data collected are to be recorded and reported as required in **Section 11**.

The following study activities/data is collected at the 8-week follow-up visit:

- Assess Treatment Outcome and recurrence of CDI
- Subject's weight
- Adverse event collection, including new onsets of obesity, metabolic syndrome, pre-diabetes, diabetes and/or autoimmune disorders
- Changes to concomitant medications since the last visit
- Cdiff32 health-related quality of life questionnaire completed by the subject
- Record employment status
- For subjects who consented to the Optional Stool Sample collection, remind the subject to collect and ship a stool sample to Rebiotix

10.12. 4- and 6-Month Telephone Assessments

These phone calls must occur within the window of ± 14 days (see **Table 10-1**). All safety data collected are to be recorded and reported as required in **Section 11**. Prior to the call, mail out the Cdiff32 health-related quality of life questionnaire to the subject for completion, including the return, addressed and stamped envelope.

The following study activities/data will be collected at the telephone assessment calls:

- Assess recurrence of CDI
- Subject's weight, self-reported

- Adverse event collection, including new onsets of obesity, metabolic syndrome, pre-diabetes, diabetes and/or autoimmune disorders
- Changes to concomitant medications since the last visit
- Remind the subject to complete the Cdiff32 health-related quality of life questionnaire, if not received prior to the telephone visit.
- Record employment status
- For subjects who consented to the Optional Stool Sample collection, remind the subject to collect and ship a stool sample to Rebiotix

The last phone call will occur 6 months after the date of the last administration of IP.

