10.14. Second RBX2660 Treatment

Subjects with a documented treatment failure meeting the protocol definition (**Section 7.3.6**) after receipt of the first RBX2660 enema may be scheduled for administration of a second RBX2660 enema. If antibiotics are given to control symptoms, a 24-72 hour washout period prior to administration of a second RBX2660 enema is required, however the second enema must be administered within 21 calendar days of failure determination.

In order to receive the second treatment with RBX2660, a subject must have documentation of the following:

- Meeting all treatment failure criteria as defined by the protocol (**Section 7.3.6**)
- Compliance to the washout period (discontinuation of antibiotics for 24-72 hours prior to administration visit) is confirmed, if applicable
- Negative urine-dipstick pregnancy test for subject of childbearing potential to confirm that they are not pregnant on the date of administration
- Enema administration is to occur within 21 calendar days of failure determination

The following study activities/data will be collected at this visit prior to IP administration:

- Onsite urine pregnancy test for subjects of child bearing potential
- Assess vital signs: temperature, pulse, blood pressure, respiration
- Changes to concomitant medications since the last visit
- Assess recurrence of CDI
- Assess for adverse events since enrollment
- Date and time of the last bowel movement prior to the enema
- Did the subject void his/her bladder prior to entering the administration room

Following successful completion of the above listed items, IP is administered via enema per the Instructions for Use and standard site procedure; see **Section 9.8.3**.

The following information is collected specific to the administration of the IP:

- Enema clinical batch number
- Enema administration start and end time
- Enema administration status (successful; attempted, not completed; opened, not administered)
- Subject position for enema
 - Length of time subject was in position after enema
- Did the Rebiotix kit components perform as expected
- Note whether the subject expelled or leaked any of the IP during the observation period
 - How long was the enema retained before the expulsion or leakage (minutes)
 - What was the estimated amount of enema that was expelled or leaked

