Subjects remain at the site under supervision for at least one hour post-IP administration for vital sign assessment (temperature, heart rate, blood pressure, respiratory rate) about every 15 minutes and observation. If the subject's vital signs do not return to the Baseline visit's (**Section 10.8**) pre-administration values $\pm 20\%$, assess the subject for a possible AE.

All safety data collected are to be recorded and reported as required in **Section 11**.

If a subject receives a second RBX2660 enema, follow-up is completed via telephone assessment at 1-week, 4-weeks, 8-weeks, and 6 months per **Section 10.14.1** after the second RBX2660 treatment.

No additional treatments of RBX2660 beyond a second enema will be administered as part of this study for treatment failures.

The study will be considered complete when all subjects have reached their 6-month follow-up after the last study enema received, including second enemas, or have exited, whichever is earlier.

10.14.1. 1-week, 4-weeks, 8-weeks, 6-month Telephone Assessment

- Subject's weight, self-reported
- Adverse event collection, including new onsets of obesity, metabolic syndrome, pre-diabetes, diabetes and/or autoimmune disorders
- Changes to concomitant medications since the last visit
- For subjects who consented to the Optional Stool Sample collection, remind the subject to collect and ship a stool sample to Rebiotix

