11.3. Anticipated Adverse Events

The following is list of anticipated AEs that may or may not be causally related to IP, the enema procedure, or CDI:

- gas (flatulence)
- belching
- abdominal distension or bloating
- increased diarrhea
- abdominal cramping or pain
- constipation
- colitis
- fever $\geq 37.8^{\circ}$ C (100.0°F)
- fatigue
- chills

- transmission of disease from the donor to recipient
- rectal irritation or pain
- rectal bleeding
- nausea
- vomiting
- hypotension
- puncture of the intestine

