Abdominal cramping/pain	Discomfort/pain causing no or minimal interference with usual social and functional activities	Discomfort/pain causing greater than minimal interference with usual social and functional activities	Discomfort/pain causing inability to perform usual social and functional activities	Disabling pain causing inability to perform basic self-care OR inpatient hospitalization \geq 24 hours
Constipation	Occasional or intermittent symptoms, occasional use of stool softeners, laxatives, dietary modifications or enema	Persistent symptoms with regular use of laxatives or enemas indicated	Symptoms causing inability to perform usual social and/or functional activities	Life-threatening consequences, e.g., obstruction, toxic megacolon
Colitis	No symptoms, regardless of pathologic or radiographic evidence of inflammation	Abdominal pain, mucus or blood in the stool	Abdominal pain, fever, change in bowel habits with ileus; peritoneal signs	Life-threatening consequences, e.g., perforation, bleeding, ischemia, necrosis, toxic megacolon
Fever	37.8 – 38.6°C (100.0 – 101.5° F)	38.7 – 39.3°C (101.6 – 102.8° F)	39.4 – 40.5°C (102.9 – 104.9° F)	> 40.5°C (104.9° F)
Fatigue/ malaise	Symptoms causing no or minimal interference with usual social and functional activities	Symptoms causing greater than minimal interference with usual social and functional activities	Symptoms causing inability to perform usual social and functional activities	Incapacitating fatigue/malaise symptoms causing inability to perform basic self-care functions
Chills	Symptoms causing no or minimal interference with usual social and functional activities	Symptoms causing greater than minimal interference with usual social and functional activities	Symptoms causing inability to perform usual social and functional activities	NA
Rectal discomfort or irritation	No symptoms or symptoms not requiring medical intervention	Symptomatic with medical intervention (topical medications / treatments) indicated	Symptoms causing inability to perform usual social and functional activities or requiring medical intervention other than topical medications / treatments	NA

Parameter	Grade 1: Mild	Grade 2: Moderate	Grade 3: Severe	Grade 4: Potentially Life-threatening
Rectal bleeding	Mild or intermittent without transfusion	Persistent without transfusion	Requires transfusion	Life-threatening consequences

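### The ±20% vital-sign prompt after the enema cannot respond to a Grade 1–3 fever, and at the second enema it is referred to the first enema's values.

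*Protocol*

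**What the plan says.** Protocol 10.8 keeps the subject on site for at least one hour after the enema, with "vital sign assessment (temperature, heart rate, blood pressure, respiratory rate) about every 15 minutes and observation". The next sentence is the trigger: "If the subject's vital signs do not return to the pre-administration values $\pm 20\%$, assess the subject for a possible AE". It makes no exception for any of the four signs.

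Protocol 10.14 repeats the one-hour observation after a second enema. Before that dose the site must "Assess vital signs: temperature, pulse, blood pressure, respiration". The trigger, however, looks back to the first enema. It applies to vital signs that "do not return to the Baseline visit's (Section 10.8) pre-administration values $\pm 20\%$, assess the subject for a possible AE".

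Elsewhere the protocol defines fever in absolute terms. Sections 11.3 and 11.4 list it from 37.8°C. Table 11-1 in 11.7 starts Grades 1, 2 and 3 at 37.8, 38.7 and 39.4°C, and Grade 4 is anything above 40.5°C.

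**The concern.** A percentage of a Celsius or Fahrenheit reading has no physical meaning, because neither scale starts at a true zero. A band that may suit pulse or blood pressure is far too wide for temperature, and its width depends on the unit used.

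The second-enema reference raises a separate problem. A check on reaction to dosing should compare readings after the dose with readings just before it. Here the same-day readings exist but are not the comparator. The subject's condition also differs between the two occasions: symptoms were controlled before the first enema, whereas the second follows confirmed CDI diarrhea, with antibiotics optional (7.5).

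The primary endpoint is the number of subjects with product- or enema-related TEAEs (6.4). Table 10-1 schedules no vital signs at routine follow-up. SAP 6.3 summarizes them only as Baseline assessments, and SAP 7.1 otherwise provides listings. Recording an AE is therefore the main way these readings reach the endpoint. SAP 6.6 reports safety separately after each enema, so a weaker prompt at the second would affect a period that is reported on its own.

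**Working it through.** The plan gives no figure for this rule to reproduce. The check is direct arithmetic.

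**Temperature.** Inputs: the ±20% band (10.8) and the fever grades (Table 11-1). The pre-enema temperature is an assumption: 35.5–37.7°C, that is, below the protocol's own 37.8°C cut-off.

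Upper limit = 1.2 × pre-enema value:
- 35.5 × 1.2 = 42.6°C
- 36.0 × 1.2 = 43.2°C
- 37.0 × 1.2 = 44.4°C
- 37.7 × 1.2 = 45.2°C

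Rise from 37.0°C to each grade limit:
- Grade 1: 37.8/37.0 − 1 = 2.2%
- Grade 2: 38.7/37.0 − 1 = 4.6%
- Grade 3: 39.4/37.0 − 1 = 6.5%
- Grade 3/4 boundary: 40.5/37.0 − 1 = 9.5%

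Even from 35.5°C, the 40.5°C boundary is a rise of only 14.1%. For 40.5°C to sit on the +20% edge, the pre-enema value would have to be 40.5/1.2 = 33.75°C or lower. Grades 1–3 therefore cannot trigger the rule. Grade 4 has no ceiling, so it can, but only above 42.6–45.2°C.

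Unit dependence: 37.0°C is 98.6°F, and 98.6 × 1.2 = 118.3°F, which is 48.0°C. The same reading taken in Celsius gives 44.4°C.

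**Second-enema reference.** Age of the reference: failure can occur up to 8 weeks after the first enema (7.3.6), and the second enema may follow within 21 calendar days of failure determination (7.5). 56 + 21 = 77 days, plus any lag between recurrence and determination.

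Illustrative values (assumed, not from the documents):
- First-enema systolic pressure 120 gives a band of 96–144. A same-day pre-dose value of 140 falling to 96 is a drop of (140 − 96)/140 = 31%, with no prompt. Referred to the same-day value, the band would be 112–168, and 96 would fall outside it.
- With the same band, a steady 145 or a steady 95 prompts an assessment although nothing changed after dosing.
- First-enema pulse 70 gives 56–84. A steady 88 prompts an assessment with no change.

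**How many second enemas.** Assume failure rates like those reported for earlier studies: 100 − 78.9 = 21.1% (5.3.3, a two-enema regimen) and 100 − 70.4 = 29.6% (5.3.4). Then 750 × 0.211 = 158 and 750 × 0.296 = 222. In the first study 15 of 16 failures took a second enema (5.3.1). Because it is optional, 158–222 is an upper range, and it counts subjects checked against the old reference, not subjects misclassified.

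**The case against.** The strongest reply is that the band only adds a prompt. It neither defines nor restricts an AE. Table 10-1 marks AE assessment at both enema visits. Section 11.1 asks for AE assessment at each visit, 11.3 lists fever from 37.8°C as an anticipated event, and 11.8 encourages entry when the investigator is unsure. After the first enema, the diary also solicits fever from the day of dosing. A supervised subject with a measured 38.5°C should be caught without the band. This stands.

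It rules out several stronger readings that a reader might infer:
- That acute reactions are missed as a general result. The documents support only that they can be under-prompted.
- That after the second enema this rule is the only objective prompt. The fever threshold and grades are numeric and not tied to the first enema.
- That no fever of any grade can breach the band. Grade 4 is open-ended.
- That the primary endpoint is biased by a known amount. A flag leads only to an assessment, and an event counts only if it is recorded as an AE and judged related.

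The reference in 10.14 could also be deliberate. Section 10.8 is cited by name, and values taken in a controlled state may seem steadier than those following a recurrence. That is arguable, but the protocol gives no such reason, and a subject who arrives outside the old band has nothing to return to.

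The reply does not rescue the rule itself. Most of the other routes rely on judgment or self-report, whereas this is the numeric trigger stated for the observation hour. The diary lists neither hypotension after the first enema nor anything after the second, where the next scheduled contact is a telephone call at one week.

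**Conclusion.** The concern holds as a conflict within the protocol that weakens AE ascertainment. The temperature arm of the prompt is effectively inert: none of Grades 1–3 can trigger it from an afebrile baseline, and Grade 4 can only above 42.6–45.2°C, given the assumed range of 35.5–37.7°C. The prompt still works for persistent changes in the other three signs at the first enema. At the second, it combines drift since the first enema, over as much as 77 days or more, with change after dosing, and can err in either direction. How often depends on how far subjects' pre-dose values shift, on which the documents give no data. The practical gap is greatest after the second enema. The change is worth making, but no figure can be put on the effect on the primary endpoint.

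**What to change.** Reconcile the ±20% sentences in Protocol 10.8 and 10.14 with the fever definition in 11.3 and 11.4 and the grades in Table 11-1, so that temperature is not judged by a percentage band. Reconcile the reference in 10.14 with the same-day pre-administration values that the section already collects, or state why first-enema values are used. This review proposes no monitoring threshold; that choice is for the sponsor.

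The cost is about two sentences of protocol text. All the measurements are already taken. The downside is that a few more readings would be reviewed as possible AEs.
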